1. The first step is to understand the pattern of missingness. In order to perform the multiple imputation, a monotone missing pattern has to be achieved. For example, if there exist values for baseline and Week 4 visits, but missing values for the Week 1 or 2 visits, the Markov-Chain Monte-Carlo (MCMC) method will be used to impute the small amount of missing data that may be missing at the intermediate visits that is required to make the missing data pattern monotone before applying the multiple imputation algorithm. This method uses a non-informative Jeffreys prior to derive the posterior mode from the expectation-maximization (EM) algorithm as the starting values for the MCMC method. The MCMC method will use the seed 6457149. The vIGA-AD score will be treated as a continuous variable for this step and the model will include the vIGA-AD scores at baseline, Week 1, Week 2, and Week 4. To avoid values that could not be observed in practice, imputed values will be rounded to the nearest integer (Round=1 option in PROC MI) in the range of 0 to 4.

To determine the number of multiply-imputed datasets to be created at this step, the proportion of datapoints with non-monotone pattern across all visits and subjects will first be derived as follows:

$$\frac{\text{number of non monotone visits accross all visits and subjects}}{\text{total number of expected visits across all subjects}} * 100$$

Then, the following table will be used:

	STATISTICAL ANALYSIS PLAN, Version 3.0
Protocol Number: ARQ-151-311	Sponsor: Arcutis Biotherapeutics, Inc.

Non-monotone Missing Data	Number of Imputed Datasets
$\leq 2\%$	1
$> 2\% \text{ to } \leq 5\%$	3
$> 5\%$	10

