2. Once the monotone pattern is achieved, the next step is to implement the imputation algorithm. For this, the PMM regression method will be used. This method is particularly helpful if the normality assumption is violated. For subjects with complete data up to a particular visit, a PMM regression model will be fit that includes the outcome at that visit as the dependent variable and as independent variables, the treatment group, pooled study site, and vIGA-AD score outcomes at previous visits, using a seed of 482371. For other scales/questionnaires, the actual baseline vIGA score will also be included as an independent variable. This process will be repeated 25 times, resulting in a total of 25 to 250 complete analysis datasets, depending on the number of imputed monotone datasets that are required. The seed may be changed after unblinding in case of any issues with the imputation process, and it will be documented in the CSR if any change is required.
3. For each of the 25 to 250 completed dataset, the necessary derived variable will be computed as defined in Section 5.5 and analyzed using a CMH analysis, adjusted for the pooled study site and randomized vIGA-AD score for the primary efficacy endpoint and adjusted for the pooled site for the secondary efficacy endpoint. Results will be combined into one multiple imputation inference as follows:
 - a. Common proportion of success, common Mantel-Haenszel (MH) proportion difference (and associated 95% CI), and common MH odds ratio (and associated common 95% CI) will be combined using PROC MIANALYZE based on Rubin's rule. Common MH odds ratios and associated common 95% CI will first be normalized using a log-transformation before being combined using PROC MIANALYZE. The resulting combined common MH odds ratio and associated combined common 95% CI will be back-transformed to the arithmetic scale before being presented in a table.
 - b. For the combined common proportion of success, the associated combined common 95% CI will be calculated as per Lott and Reiter multiple imputation Wilson interval method¹.
 - c. Two p-values will be produced for each analysis:
 - i. The primary p-value will be obtained from a multiple imputation CMH test, where CMH general association statistics and their standard errors obtained

	STATISTICAL ANALYSIS PLAN, Version 3.0
Protocol Number: ARQ-151-311	Sponsor: Arcutis Biotherapeutics, Inc.

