from the analysis of each multiply-imputed dataset will be transformed as per Wilson-Hilferty² before being combined using PROC MIANALYZE based on Rubin's rule. Because the Wilson-Hilferty transformation is a monotone transformation, the p-value for the CMH test is the one-sided p-value from the t distribution. This p-value will be the primary p-value used to evaluate the result according to the multiple testing strategy described in Section 6.5.

- i. Should the common MH odds ratio from the analysis of at least one of the multiply-imputed datasets be not estimable, combined common MH odds ratio and associated combined common 95% CI and p-value will not be presented. Under such circumstance, conclusions will be based on the p-value obtained from a multiple imputation test of the proportion difference, where the common proportion difference using MH weights and associated common standard errors based on the Sato variance estimator obtained from the analysis of each multiply-imputed dataset will be combined using PROC MIANALYZE based on Rubin's rule.

Similar multiple imputation method will be used for the average weekly WI-NRS and EASI total score.

For the average weekly WI-NRS (refer to Section 5.5), it's the missing average weekly WI-NRS data (i.e., those that cannot be computed because only 3 or less non-missing assessments are available during a given week) at Weeks 1, 2, 3, and 4 that will be multiply imputed, not the missing daily WI-NRS data. Since the missing average weekly WI-NRS values have a precision of 1 decimal place, the MCMC imputation for the non-monotone missing data will be restricted to values between 0 and 10, rounded to the 1st decimal (i.e., 0.1). Imputation of missing data for WI-NRS will be based on the ITT population, i.e., all randomized subjects will be included in the imputation process.

For the EASI total score (refer to Section 5.5), it's the missing EASI total score data at Weeks 1, 2, and 4 that will be imputed, not the missing EASI question score data. Since the missing EASI total scores have a precision of 1 decimal place, the MCMC imputation for the non-monotone missing data will be restricted to values between 0 and 72, rounded to the 1st decimal (i.e., 0.1). Imputation of missing data for EASI total score will be based on the ITT population.

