6.5 Multiple Comparisons/Multiplicity

To control for familywise type I error at level of 0.05, the secondary endpoint of vIGA-AD Success at Week 4 for subjects with vIGA-AD score of ‘Moderate’ at randomization will only be tested if the primary endpoint demonstrates statistical significance. In addition, the remaining secondary endpoints will be inferentially tested only if the primary and the secondary endpoint (vIGA-AD Success at Week 4 for subjects with vIGA-AD score of ‘Moderate’ at randomization) comparisons are statistically significant using hierarchical testing procedure by partitioning of alpha.

Upon successful demonstration of statistical significance for the primary and above secondary endpoint, the remaining endpoints will be grouped into secondary endpoint family 1, comprised of the 4-point reduction on the WI-NRS endpoint, at Week 4, Week 2 and Week 1, and secondary endpoint family 2, comprised of the endpoints of EASI-75 at Week 4, vIGA-AD of ‘clear’ or ‘almost clear’ at Week 4, vIGA-AD of success at Week 2 and Week 1, vIGA-AD of ‘clear’ or ‘almost clear’ at Week 2 and Week 1. An alpha level of 0.03 will be used to test the endpoints in the secondary endpoint family 1 sequentially. An alpha level of 0.02 will be used to test the endpoints in secondary endpoint family 2 sequentially.

	STATISTICAL ANALYSIS PLAN, Version 3.0
Protocol Number: ARQ-151-311	Sponsor: Arcutis Biotherapeutics, Inc.

In addition to the partitioning of the overall 0.05 alpha into two families, the Fallback Method will be applied. The fallback method is a modification of the fixed-sequence method, providing opportunity to test an endpoint later in the sequence even if an endpoint tested early in the sequence has failed to show statistical significance. The order of the endpoints remains important. The appeal of the fallback method is that if an endpoint later in the sequence has a robust treatment effect while the preceding endpoint is unsuccessful, there is a modest amount of alpha retained as a fallback to allow interpretation of that endpoint without inflating the Type I error rate. Applying the fallback method begins by dividing the total alpha (not necessarily equally) among the endpoints and maintains a fixed sequence for the testing. In this study, the Fallback Method will be applied to the fixed sequence of testing Family 1, and then Family 2.

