12.2 Secondary Endpoints Analysis

Secondary efficacy endpoints are based on the vIGA-AD scale, WI-NRS scale or EASI questionnaire. The list of secondary efficacy endpoints can be found in Section 2 and their derivation in Section 5.5.

- For more details about the vIGA-AD scale refers to Section 12.1.1.
- The WI-NRS scale is a single item scale assessing the subject-reported worst itch severity during the previous 24-hour period. The scale is from 0 to 10 ('no itch' to 'worst itch imaginable').
- For the EASI questionnaire, four anatomic sites (head, upper extremities, trunk, and lower extremities) are assessed for erythema, induration/infiltration (papules), excoriation, and lichenification as seen on the day of the examination. The severity of each sign is assessed using a 4-point scale (half steps are allowed e.g., 0.5): 0 (none), 1 (mild), 2 (moderate), and 3 (severe). The area affected by AD within a given anatomic site is estimated as a percentage of the total area of that anatomic site and assigned a numerical value according to the degree of AD involvement as follows: 0 (no involvement), 1 (1-9%), 2 (10-29%), 3 (30-49%), 4 (50-69%), 5 (70-89%), and 6 (90-100%).

For each secondary efficacy endpoint, missing data will be imputed and data will be summarized as for the primary efficacy endpoint (refer to Section 12.1.3).

Upon successful demonstration of statistical significance for the primary efficacy endpoint, the secondary efficacy endpoint of vIGA-AD success among subjects with vIGA-AD score of 'Moderate' at randomization will be analyzed as described for the primary efficacy endpoint (refer to Section 12.1.3) but based on the vIGA-AD Moderate ITT population (refer to Section 4.4) and stratifying by pooled study site only. That is, as per the vIGA-AD Moderate ITT population definition all subjects included in this analysis will have a randomized vIGA-AD score of Moderate (3) and so, the CMH test cannot be stratified by randomized vIGA-AD score.

Upon successful demonstration of statistical significance for the primary and above secondary efficacy endpoints, the remaining secondary efficacy endpoints will be grouped into secondary

	STATISTICAL ANALYSIS PLAN, Version 3.0
Protocol Number: ARQ-151-311	Sponsor: Arcutis Biotherapeutics, Inc.

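### SAP 6.2.1 step 1 fills intermittent Week 1 and Week 2 gaps without using treatment group, so a small bias enters alpha-controlled early comparisons

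*SAP*

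**What the plan says.** SAP 6.2.1 specifies step 1 closely (prior, starting values, seed, rounding) and closes the variable list for vIGA-AD: "the model will include the vIGA-AD scores at baseline, Week 1, Week 2, and Week 4". It mentions neither treatment nor a run by arm. The stated purpose of the step: "impute the small amount of missing data that may be missing at the intermediate visits that is required to make the missing data pattern monotone".

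Step 2 is a predictive mean matching regression. Its independent variables are "the treatment group, pooled study site, and vIGA-AD score outcomes at previous visits". The two steps therefore differ, as written, in whether the subject's arm is used.

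For the other scales the SAP states: "Similar multiple imputation method will be used for the average weekly WI-NRS and EASI total score". For itch it is the weekly averages "at Weeks 1, 2, 3, and 4 that will be multiply imputed, not the missing daily WI-NRS data". MCMC is again used for non-monotone gaps, and its variables are not listed.

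These imputed values are tested. SAP 12.2 states: "For each secondary efficacy endpoint, missing data will be imputed and data will be summarized as for the primary efficacy endpoint". SAP 6.5 puts the WI-NRS 4-point response at Weeks 4, 2 and 1 in Family 1: "An alpha level of 0.03 will be used to test the endpoints in the secondary endpoint family 1 sequentially". Family 2, at alpha 0.02 (0.05 if all of Family 1 succeeds), includes "vIGA-AD of success at Week 2 and Week 1, vIGA-AD of ‘clear’ or ‘almost clear’ at Week 2 and Week 1".

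**The concern.** An imputation model should contain the comparison that will be tested on the completed data. Step 1 fits one regression to both arms pooled. A subject with a Week 1 or Week 2 gap and a later observed score receives a value predicted from baseline and the other visits. Those scores carry some of the treatment effect, but not necessarily the right amount for the missing visit. Step 2 does not revisit the value, so the error passes straight into the early comparison.

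The early tests also have a role beyond their own claims. WI-NRS at Week 1 is the last test in Family 1, and only if all three succeed is 0.03 of alpha passed on, so that Family 2 is tested at 0.05 rather than 0.02.

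No planned sensitivity analysis varies step 1. The tipping-point analysis (SAP 6.2.3) leaves step 1 unchanged and covers only the two Week 4 vIGA-AD success endpoints.

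**Working it through.** **The plan's own figure.** Step 1 yields 1, 3 or 10 datasets and step 2 repeats 25 times: 25 × 1 = 25, 25 × 3 = 75, 25 × 10 = 250. This reproduces the stated 25 to 250 and is not in dispute.

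**Inputs from the documents.** Allocation is 2:1 (SAP 3.4), the alphas are 0.03 and 0.02 (SAP 6.5), and the model variables are as above.

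**Inputs assumed, because the documents do not give them.** Mean treatment differences by visit and SDs are in the table. Visit correlation ρ is 0.4, 0.6 or 0.8, either AR(1) by visit order or exchangeable. The baseline difference is 0.

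**Bias among imputed values.** Let d be the vector of mean differences, Σ the within-arm covariance and p = 2/3 the share on active. With treatment omitted, step 1 works from the pooled covariance C = Σ + p(1 − p)dd′, where p(1 − p) = 2/9. The imputed difference at the missing visit t, given the other visits o (baseline included), is d_o′ C_oo⁻¹ C_ot. Dividing by the true difference gives r, the share kept:

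| Assumed differences (SD) | Week 1, AR(1) | Week 1, exchangeable | Week 2, AR(1) | Week 2, exchangeable |
|---|---|---|---|---|
| vIGA-AD 0.3/0.4/0.45 (0.85) | 0.50, 0.62, 0.68 | 0.66, 0.80, 0.89 | 0.67, 0.84, 0.92 | 0.46, 0.56, 0.64 |
| vIGA-AD 0.4/0.4/0.4 (0.85) | 0.39, 0.48, 0.53 | 0.49, 0.59, 0.68 | 0.72, 0.89, 0.98 | 0.49, 0.59, 0.68 |
| WI-NRS 0.6/0.9/1.1/1.2 (2.2) | 0.56, 0.69, 0.75 | 0.97, 1.12, 1.21 | 0.68, 0.85, 0.93 | 0.63, 0.73, 0.80 |
| WI-NRS 0.4/0.8/1.1/1.3 (2.0) | 0.72, 0.89, 0.98 | 1.39, 1.60, 1.67 | 0.68, 0.84, 0.92 | 0.68, 0.79, 0.87 |

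Each cell gives r at ρ = 0.4, 0.6 and 0.8. Week 2 runs from 0.46 to 0.98 and Week 1 from 0.39 to 1.67.

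A strongly back-loaded pattern (vIGA-AD 0/0.2/0.45) marks the edge of these ranges. A difference of 0.07 to 0.17 points appears among imputed Week 1 values where none exists (0.08 to 0.27 if baseline is left out of the regression), and r at Week 2 is 0.54 to 1.09.

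**Effect on the whole comparison.** With a share m imputed, the overall difference is the true one times 1 − m(1 − r). A simulation with integer scores and a rounded regression draw (not the full MCMC) gives one vIGA-AD Week 2 case (flat 0.4, AR(1), ρ = 0.4) with a true success difference of 13.9 points, and 8.5 among imputed values without treatment:
- m = 2%: 0.98 × 13.9 + 0.02 × 8.5 = 13.79
- m = 5%: 0.95 × 13.9 + 0.05 × 8.5 = 13.63
- m = 10%: 0.90 × 13.9 + 0.10 × 8.5 = 13.36

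With treatment in the model, the imputed mean difference in the simulations is 97–99% of the true one.

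**Effect on power.** Take an illustrative test with 90% power at two-sided alpha 0.02; the SAP states no power for the early tests. The standardised effect is 2.326 + 1.282 = 3.608. Hold the standard error fixed and set r = 0.4, near the low end of the table:
- m = 2%: 3.608 × 0.988 − 2.326 = 1.239, power 89.2%
- m = 5%: 3.608 × 0.970 − 2.326 = 1.173, power 88.0%
- m = 10%: 3.608 × 0.940 − 2.326 = 1.065, power 85.7%

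At alpha 0.03 the figures are 89.3%, 88.1% and 85.9%. At the other extreme, r = 1.67 with m = 5% overstates the difference by 0.05 × 0.67 = 3.4%.

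**The case against.** The case for leaving the SAP alone has four parts.

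- **Few values are affected.** The SAP expects little intermittent missingness, and at 5% or less the change is a few tenths of a percentage point. This stands and is why the point is minor. A reader might infer from the rule that a diary week needs at least 4 entries that gaps will be common. No document gives a rate; the SAP only provides a tier for more than 5%.
- **Other analyses avoid step 1.** Non-responder and observed-data analyses are planned for these endpoints and run when the hierarchy allows, which is when an early claim could be made. This stands as mitigation, but neither analysis corrects the main estimate or its p-value.
- **For WI-NRS the omission is inferred.** The SAP says only that the method is similar. This is fair. If treatment was intended there, the text should say so.
- **The error is conservative.** A reader might infer that pooling the arms always pulls imputed values together and so attenuates both Week 1 and Week 2. The calculation does not support that. Later scores carry the larger later effect back to Week 1, where the imputed difference can exceed the truth. Only when treatment has no effect at any visit does the omission do no harm.

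Two wider readings also fail. Week 3 exists only for WI-NRS and is not a tested endpoint. The only confirmatory EASI endpoint is EASI-75 at Week 4, and step 1 fills intermediate visits only, so no EASI value that it fills is itself tested.

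**Conclusion.** The point holds as a small, avoidable defect. As written, step 1 ignores treatment for vIGA-AD, and by extension apparently for WI-NRS, while the values it fills are used in alpha-controlled Week 1 and Week 2 tests. Among filled values the Week 2 difference was diluted in all four main effect patterns, and the Week 1 difference was usually diluted but sometimes overstated. These ranges rest wholly on assumed effects, SDs and correlations. The overall consequence is that bias times the share imputed: about 1 to 4 points of power at 2% to 10% imputed when only 40% of the effect is kept.

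It would be wrong to conclude that the primary result is in doubt. The primary endpoint, the Moderate-subset endpoint and the other Week 4 endpoints, EASI-75 included, are touched only through Week 1 to 3 values used as predictors in step 2, which has treatment in its model.

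**What to change.** In SAP 6.2.1 step 1, add treatment group to the MCMC model, or state that the step is run separately by treatment group. Say that this applies to vIGA-AD and WI-NRS, and to EASI for consistency.

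The cost is one clause and about one line of code. At 2:1 of about 650 subjects, the arms hold about 433 and 217, ample for a model with four or five score variables. Step 2 already uses treatment codes, so no new blinding question arises. Sample size, alpha, endpoints and study conduct do not change.

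### With 2% or less non-monotone data, intermittently missing Week 1 and Week 2 values are imputed once and held fixed over all 25 datasets, so their uncertainty is left out of six confirmatory early tests

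*SAP*

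**What the plan says.** SAP 6.2.1 imputes in two stages.

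- **Step 1 (MCMC)** makes the missing-data pattern monotone. Its task is to "impute the small amount of missing data that may be missing at the intermediate visits". For vIGA-AD, "the model will include the vIGA-AD scores at baseline, Week 1, Week 2, and Week 4"; neither treatment nor site is listed. The seed is fixed: "The MCMC method will use the seed 6457149". A table headed "Number of Imputed Datasets" sets how many monotone datasets are made: 1 at 2% or less non-monotone data, 3 above 2% and up to 5%, and 10 above 5%. The percentage is taken over all expected visits of all subjects: "the proportion of datapoints with non-monotone pattern across all visits and subjects will first be derived as follows".
- **Step 2 (PMM)** fills what is still missing, visit by visit: "For subjects with complete data up to a particular visit, a PMM regression model will be fit". Then: "This process will be repeated 25 times, resulting in a total of 25 to 250 complete analysis datasets".

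The results are combined by Rubin's rule. The same approach applies to the weekly WI-NRS and to EASI, and SAP 12.2 applies it to every secondary endpoint.

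**The concern.** Rubin's rule measures imputation uncertainty by how much the completed datasets differ. A value drawn once and copied into all 25 datasets does not differ between them. In the lowest band, therefore, the intermittent gaps are singly imputed, and repeating the PMM step does not change that.

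SAP 6.5 and 12.2 list six alpha-controlled tests that use such values: the WI-NRS 4-point reduction, vIGA-AD Success, and vIGA-AD clear or almost clear, each at Weeks 2 and 1. Both families are tested in sequence. A WI-NRS p-value above 0.03 at Week 2 or Week 1 also stops Family 1 and blocks the carry-over of 0.03. Family 2, which opens with EASI-75 at Week 4, is then tested at 0.02 instead of 0.05. A borderline early result that turns on the draw could thus have effects further down the hierarchy.

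**Working it through.** **1. The plan's own figure.** MCMC datasets times PMM repeats: 1 × 25 = 25, 3 × 25 = 75, 10 × 25 = 250. This reproduces the stated range of 25 to 250.

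**2. Which values are held fixed.** Step 1 fills a gap only if a later visit is observed.
- Intermittent gap at Week 1 or 2 (or Week 3 for WI-NRS): filled in step 1, so one value in the lowest band.
- Gap at Week 1 or 2 through dropout: filled in step 2, so 25 draws.
- Discontinuation for adverse event or lack of efficacy: non-responder under SAP 5.5.
- Week 4: the last visit, so never filled in step 1. Step 1 values reach it only as predictors in step 2.

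**3. How many values the 2% band allows** (650 subjects, SAP 5.1).
- vIGA-AD, three post-baseline visits: 0.02 × 650 × 3 = 39. All at one week: 39/650 = 6%. Split evenly over Weeks 1 and 2: 19.5 each, or 3%.
- vIGA-AD if baseline visits are also counted: 0.02 × 650 × 4 = 52, at most 52/650 = 8% of one week.
- WI-NRS, four weekly values, or five with baseline: 52 or 65, at most 8% or 10% of one week among all randomised subjects. The WI-NRS tests use a subset whose size the documents do not give, so the share there may differ.

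**4. Noise from one draw.** The documents give no early response rates, correlations between visits or gap counts, so these are assumptions. Two simulations used 650 subjects, a normal-model draw of Week 1 vIGA-AD given baseline, Week 2 and Week 4, rounding to 0-4, and a stratified CMH z for Week 1 Success. The first assumed success of 14% against 9%. The second used 2:1 allocation, 40 strata, about 10% with vehicle and about 10% or 15% with active, correlations between post-baseline visits of about 0.5-0.6, and gaps at random.

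| Fixed values at Week 1 | Reading | SD of z across single draws |
|---|---|---|
| 19 | 2% split over Weeks 1 and 2 | 0.15-0.16 |
| 39 | 2%, all at one week (worst case) | 0.21 (first), 0.23-0.24 (second) |
| 52 | as above, baseline visits counted | 0.25-0.28 |

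**5. What that means for a p-value.** Two-sided p = 0.020 corresponds to z = 2.326.
- SD 0.24: z from 2.086 to 2.566, so p from 0.037 to 0.010.
- SD 0.15: z from 2.176 to 2.476, so p from 0.030 to 0.013.
- With 25 independent draws the SD is divided by √25: 0.24/5 = 0.048 and 0.15/5 = 0.03. In the larger case p runs from about 0.018 to 0.023.

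**6. Type I error.** Under no effect, with 39 fixed values and one draw, the second simulation (10,000 runs) rejected in 0.021, 0.030 and 0.052 of runs at alpha 0.02, 0.03 and 0.05. The same data without gaps gave 0.020, 0.031 and 0.052. A separate null simulation (20,000 runs) gave 0.0217, 0.0319 and 0.0530, with an SD of z of 1.009.

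**7. The other two bands.** With 3 or 10 MCMC datasets, the 25 PMM draws within each share their step 1 values, yet all 75 or 250 datasets are pooled as if independent. Under assumed between-draw variances, this understates the standard error by about 0.3-1.5%.

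**The case against.** The strongest reply is that this is Monte Carlo noise under a prespecified seed, in a small part of the data, with no measurable loss of type I error. Most of that stands.

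- A reader might infer that the early endpoints rest on one random draw. They do not: for vIGA-AD, at least 92-94% of values at each early visit are observed, handled by the discontinuation rule or redrawn 25 times.
- A reader might infer inflated alpha because a variance component is missing. The simulations do not show it. The step 1 model has no treatment term, so under the null its noise is common to both arms.
- A reader might extend the point to the primary endpoint or to EASI-75 at Week 4. Step 1 never fills a Week 4 value.
- The 39-gap case is a ceiling, and the SAP expects few intermittent gaps. With 5 to 10 gaps the simulated SD of z was 0.07-0.10.
- SAP 12.2 plans non-responder and observed-data analyses that do not use step 1.

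Three things remain. The supportive analyses of these endpoints are run only if the testing hierarchy allows, so they may be absent just where an early test narrowly failed. The SAP also says: "The seed may be changed after unblinding in case of any issues with the imputation process". It requires any change to be documented and does not say which of the two seeds is meant. This is no evidence of an intent to choose a seed, but a p-value that moves little with the seed makes the question moot. Finally, the few gaps expected do not justify single imputation when multiple draws cost nothing.

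**Conclusion.** The point holds as a minor refinement. In the lowest band the plan singly imputes intermittent gaps and leaves their uncertainty out of the pooled variance of six alpha-controlled tests at Weeks 1 and 2. The result depends in part on one MCMC draw, and the likely size runs from an SD of z of about 0.15 (even split at the 2% limit) to 0.21-0.24 (every gap at one week), and less with fewer gaps. This matters only for a result near its threshold.

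These sizes rest on assumed rates, correlations and gap counts, were simulated for Week 1 vIGA-AD Success without dropout, and were not simulated for WI-NRS. With type I error close to nominal, the defect concerns reproducibility and a small omitted variance. The documents do not support calling it alpha inflation or a threat to the primary analysis. The nesting in the upper bands is smaller still.

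**What to change.** In SAP 6.2.1, delete the table that links the number of datasets to the percentage of non-monotone data. In every case, create the same number of MCMC monotone datasets, at least 25 and for example 100, and make one PMM draw in each. The completed datasets are then independent imputations, the ordinary Rubin's rule applies, and step 1 uncertainty enters the intervals. Use the same rule for WI-NRS and EASI, and for the tipping point analysis in 6.2.3, which reuses step 1. Align the dataset counts in steps 2 and 3 and in 12.1.3.

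The cost is SAP wording before unblinding and a few minutes of computing. A total of 25 or 100 stays within the planned 25 to 250, and no data collection, endpoint or alpha allocation changes.
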